3.1. Primary Endpoints

Proportion of patients who develop respiratory failure (as defined elsewhere in the protocol) or death during hospitalization for COVID-19 infection within 30 days of registration

3.2. Secondary Endpoints

- Time from study initiation to 48 hours fever-free (<100.5 degrees F orally)
- Duration of hospitalization
- Time in ICU
- Time to ICU admission
- Number of days requiring supplemental oxygen (or supplemental oxygen above baseline levels)
- Total days of mechanical ventilation
- Time to mechanical ventilation
- Shock and need for pressure support

- Incidence of any infection (viral, fungal, bacterial) including opportunistic infections
- Time to clinical resolution
- Grade 3 or higher toxicity
- Viral clearance at the end of therapy
- Time to viral clearance
- Overall survival at 3 and 12 months

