	
 • Measurement of T-cell repertoire and IgM, IgA, IgG response to SARS-CoV-2 over time among patients treated with ibrutinib (Arm A) versus control (Arm B) treatment; • Measurement of epigenetic age, clonal hematopoiesis, and MBL on treatment outcome • Measurement of serial change cytokines including (but not limited to) IL6, IL1B, TNF-alpha, IL-10 serum levels over time among patients treated with ibrutinib (Arm A) versus control (Arm B) treatment
Statistics/ Sample Size Estimate	
Safety Lead-In: 12 patients will be enrolled as part of the safety lead-in cohort. Enrollment to a dose level will stop if 2 of the first 3 evaluable patients or if at least 33% of subsequent evaluable patients (i.e, 2/6, 3/9, or 4/12) have DLT.
 
Randomized Phase 2: Allowing for roughly 10% over-accrual, we plan to randomize 66 high-risk patients with cancer to the two arms of the study in a 1:1 ratio utilizing a permuted block schedule. Randomization will be stratified on age (<60 years vs \geq 60 years) and presence of comorbidities (yes vs no) (comorbidities defined in Appendix C). The primary endpoint is the proportion of randomized patients with respiratory failure or death during hospitalization for COVID-19 infection within 30 days of registration.
 
Based on the study in China, we assume that the event rate is 40% and that it can be reduced to 15% when Ibrutinib is given in addition to standard care for COVID-19. With 60 patients and using a standard group sequential design, there is 82.8% power to detect a reduction in the event rate under the alternative hypothesis and constraining the one-sided type I error to 20%. Power was calculated using a z-test for the difference in two proportions, pooled variance, and adjustment for small sample sizes with the Casagrande-Pike-Smith correction (EAST v6.5; Cytel, Inc). There will be an interim analysis when 50% of randomized patients have been followed for 30 days from registration. The study will be stopped early if at the interim analysis the observed event rate is higher in the ibrutinib arm (Arm A) than in the control arm (Arm B). At the final analysis, data will be analyzed using a one-sided Fisher's exact test and a promising signal declared if $p \leq 0.20$ and the event rate is lower in the experimental arm.

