2.2 Secondary Objectives

- To determine time to clinical resolution of need for supplemental oxygen (i.e. maintenance of oxygen saturation of 93% or greater on room air with ambulation) or need for supplemental oxygen above baseline for those on home oxygen.
- To determine rate of ICU admission and length of ICU admission for patients treated with ibrutinib (Arm A) versus control population receiving standard therapy (Arm B)
- To determine rate of shock requiring vasopressor support for patients treated with ibrutinib (Arm A) versus control population receiving standard therapy (Arm B)
- To determine the rate of secondary infection (bacterial, fungal, viral) for patients treated with ibrutinib (Arm A) versus control population receiving standard therapy (Arm B)
- To determine the time to hospital discharge for patients treated with ibrutinib (Arm A) versus control population receiving standard therapy (Arm B)
- To determine grade 3 or higher toxicity observed in patients treated with ibrutinib (Arm A) versus control population receiving standard therapy (Arm B)
- To determine time to mechanical ventilation, the number of days of mechanical ventilation per patient and total observed in patients treated with ibrutinib (Arm A) versus control population receiving standard therapy (Arm B)
- To determine the overall survival at 3 and 12 months post-enrollment.

Exploratory Objectives

- To determine the time to defervescence (oral temperature<100.5 degrees F for a 48 hour time period) among patients treated with ibrutinib (Arm A) versus control population receiving standardtherapy (Arm B)
- To examine the impact of baseline clinical features (e.g. type of cancer, active therapy), duration of symptoms prior to admission and laboratory features (e.g. T cell count) on outcome for patients treated on this therapeutic study
- To determine the proportion of patients with viral clearance at end of ibrutinib therapy, time of hospital discharge and follow up thereafter among patients treated with ibrutinib (Arm A) versus control (Arm B) treatment
- To determine the time and proportion of patients who develop IgM and IgG levels toward SARS-CoV-2 treated with ibrutinib (Arm A) versus control treatment (Arm B)
- To examine immune cell subsets for absolute number, activation, exhaustion markers, and presence of maturation arrest (NK cells) at baseline and over time among patients treated with ibrutinib (Arm A) versus control (Arm B) treatment

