We note that the above stopping rules may be adjusted at any time during the conduct of the trial and in consideration of newly acquired information regarding the adverse event profile of the treatment(s) under investigation. The study team may choose to suspend

accrual because of unexpected adverse event profiles that have not met the specified rules above.

Secondary Endpoints: At the final analysis, all adverse events will be summarized by grade, type, and attribution (regardless of attribution and treatment-related) for each arm. Time-to-event endpoints such as time to discharge and overall survival will be estimated for each arm using the method of Kaplan-Meier. Medians estimates and/or estimates at specific time points will be provided with 95% confidence intervals. The proportion of patients with viral clearance at the time of hospital discharge will be estimated with 95% confidence intervals for each arm. For all biomarkers, descriptive statistics (e.g., means, medians, standard deviations, interquartile range) and graphical displays will be used to characterize central tendency and variability over time. Values will be log transformed as appropriate to reflect biologic plausibility. We will evaluate for statistical trends over time among the biologic measurements, with multiple measurements per patient, using mixed effects models. Lastly, associations between baseline characteristics and the primary endpoint will be evaluated with logistic regression, adjusting for arm. These analyses will be largely descriptive, as a result of a limited sample size.

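### Ventilator, ICU, oxygen and hospital days have no rule for death, so a treatment that saves lives can look worse on them

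*Combined protocol and SAP*

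**What the plan says.** Section 3.2 of the combined protocol and SAP lists, without window, denominator or rule for death, "Total days of mechanical ventilation", time in ICU, "Duration of hospitalization" and "Number of days requiring supplemental oxygen (or supplemental oxygen above baseline levels").

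Section 2.2 turns two of these into comparisons of ibrutinib with control. One is length of ICU stay. The other is "the number of days of mechanical ventilation per patient and total observed in patients treated with ibrutinib (Arm A") against Arm B.

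Section 13 names no summary or method for ventilator, ICU or oxygen days. For hospital stay it says: "Time-to-event endpoints such as time to discharge and overall survival will be estimated for each arm using the method of Kaplan-Meier". It does not say what happens to a patient who dies before discharge. Its missing-data rule is stated for the primary endpoint only. Section 13 closes the paragraph on secondary endpoints with: "These analyses will be largely descriptive, as a result of a limited sample size".

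No section defines support-free days, a worst score for death, or a competing-risk method. The primary endpoint does count death: "respiratory failure or death during hospitalization for COVID-19 infection within 30 days of registration".

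**The concern.** A count of days on support stops when the patient dies. Read literally, a patient who dies after 4 ventilator days scores better than a survivor who needed 14. A patient who dies without being intubated scores 0, the best possible value. The primary endpoint definition expects some such patients, because it allows respiratory failure to be diagnosed clinically where resources or code status rule out the listed measures.

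The trial aims to reduce death, so the arms are expected to differ in the very event that cuts these durations short. The protocol also makes better survival after ventilation a plausible route. Section 7.1.2 lets treatment continue after respiratory failure, and Section 7.2 provides for tube administration in ventilated patients. A comparison of raw days could then point against the arm with fewer deaths.

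**Working it through.** The documents give no figure for any of these durations, so there is nothing of the plan's own to reproduce on this point. The 82.8% power in Section 13 concerns the primary endpoint and does not enter.

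**Inputs from the documents.** 66 randomized 1:1, so 33 per arm. Design event rates for the primary composite are 40% (control) and 15% (ibrutinib), a ratio of 15/40 = 0.375.

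**Assumed inputs (not in the documents).** Ventilated patients who die have 4 ventilator days and ventilated survivors have 14. Mortality among the ventilated is 5/7 = 71% on control and 2/7 = 29% on ibrutinib. Patients never ventilated survive to day 30.

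**Step 1: equal ventilation, 7 of 33 in each arm.**
- Control total: 5×4 + 2×14 = 48 days.
- Ibrutinib total: 2×4 + 5×14 = 78 days, although there are 3 fewer deaths. 78/48 = 1.625, or 63% more.
- Mean per ventilated patient: 48/7 = 6.9 vs 78/7 = 11.1.
- Ventilator-free days to day 30, death scored 0: control (2×16 + 26×30)/33 = 24.6; ibrutinib (5×16 + 26×30)/33 = 26.1. The direction is now right.

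**Step 2: when do arm totals reverse?** The total is the number ventilated times the mean per ventilated patient. Ibrutinib's total exceeds control's only if its ventilation rate is more than 6.86/11.14 = 0.62 of control's.

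**Step 3: ventilation falls in the design's ratio.** This is a further assumption, because the 15/40 ratio is for the whole composite and not for ventilation. The ibrutinib total is 0.375×78 = 29.25 days, and 29.25/48 = 0.61, so it is about 39% lower than control. Totals now point the right way. The means per ventilated patient do not depend on how many are ventilated, so they remain 6.9 vs 11.1 and still mislead.

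**Step 4: sensitivity to the assumptions.** A second set of assumptions: 30% of control patients ventilated, mortality among the ventilated 60% (control) vs 30% (ibrutinib), survivors ventilated 14 days, death after d ventilator days. Raw days per randomized patient = ventilation rate × [mortality × d + (1 − mortality) × 14]. For d = 5 with 30% ventilated: control 0.30×(0.6×5 + 0.4×14) = 2.58; ibrutinib 0.30×(0.3×5 + 0.7×14) = 3.39.

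| d | ibrutinib ventilated 30% | 25% | 20% | break-even ventilation ratio |
|---|---|---|---|---|
| 5 | 2.58 vs 3.39 | 2.58 vs 2.82 | 2.58 vs 2.26 | 8.6/11.3 = 0.76 |
| 7 | 2.94 vs 3.57 | 2.94 vs 2.97 | 2.94 vs 2.38 | 9.8/11.9 = 0.82 |
| 10 | 3.48 vs 3.84 | 3.48 vs 3.20 | 3.48 vs 2.56 | 11.6/12.8 = 0.91 |
| 14 | 4.20 vs 4.20 | 4.20 vs 3.50 | 4.20 vs 2.80 | 14/14 = 1.00 |

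Each cell is control vs ibrutinib. Reversal needs deaths that come sooner than survivors leave the ventilator, and ventilation rates that are not far apart. Ventilator-free days to day 30 are 22.9 on control in every row. On ibrutinib they are 24.4, 25.3 and 26.2 at 30%, 25% and 20% ventilated. All favour the arm with fewer deaths.

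**Step 5: hospital stay.** There are two ways to treat a death before discharge. If death ends the stay, early death shortens it, as above. If the patient is censored at death, Kaplan-Meier treats that patient as still able to be discharged. This overstates the proportion discharged, by more in the arm with more deaths. Section 13 chooses neither, and neither is sound.

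**The case against.** Four objections deserve weight.

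First, equal ventilation in both arms sits badly with the trial's own hypothesis. Intubation with ventilation is a primary event, and 15% of 33 is about 5 patients for all primary events together, fewer than the 7 ventilated in Step 1. This stands. A reader might infer from the 48 vs 78 example that ibrutinib will look 63% worse, but the documents do not support that. They give no ventilation rate, time to death or mortality among the ventilated, and under the design's ratio the totals point the right way. What survives is that a reversal is possible, and that means among ventilated patients mislead in every case examined where deaths come sooner than survivors leave the ventilator. The phrase "per patient" is the plan's, but its denominator is not stated, so that version could be the one reported.

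Second, a reader might infer that hospital stay is handled only as a raw duration. It is not: time to discharge has a Kaplan-Meier analysis. That narrows the point but does not remove it, because death before discharge is left open.

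Third, Section 13 names no analysis for ventilator, ICU or oxygen days, so it would be too strong to say that a raw comparison was chosen there. The comparison comes from the objectives, and the gap is a missing rule.

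Fourth, no decision rests on these endpoints. The signal, futility and sample-size rules all use the primary endpoint, overall survival is reported separately, and the analyses are called largely descriptive. This limits the consequence. It does not make a descriptive figure that can point the wrong way useful in a small signal-finding trial.

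**Conclusion.** The point holds in a limited form and is a cheap improvement. As listed, ventilator, ICU and oxygen days reward early death, and "Duration of hospitalization" does the same. Whether arm totals reverse depends on inputs that the documents do not give. Under the first set of assumptions, ibrutinib's ventilation rate must exceed about 62% of control's; under the second, 76% to 91% for deaths after 5 to 10 ventilator days. The totals range from 48 vs 78 days with equal ventilation to about 39% lower on ibrutinib with ventilation in the 15/40 ratio. Means among ventilated patients are wrong-way throughout (6.9 vs 11.1).

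This should not be read as a flaw in the trial's main result. The primary composite counts death, and its test, power and sample size are unaffected.

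**What to change.** Amend Sections 3.2 and 13 as follows.

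- For all randomized patients, analyse days alive and free of ventilation, of ICU, of supplemental oxygen (above baseline for home-oxygen users) and of hospital, through day 30. Score death by day 30 as 0. Day 30 is suggested because it matches the primary endpoint; Section 3.2 gives these durations no window.
- Show the number of deaths by arm beside each of these measures.
- Estimate time to discharge by cumulative incidence, with death as a competing event, in place of Kaplan-Meier.
- Keep raw durations as description only, split into survivors and non-survivors, with the denominator stated.

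The cost is wording. Deaths are already captured as serious adverse events and for overall survival, and the study calendar has a one-month contact. That contact should confirm any readmission and home oxygen up to day 30. No change in sample size is needed. The downside is that each measure combines death with duration, which is why deaths must be shown alongside.

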11. BIOMARKER, CORRELATIVE, AND SPECIAL STUDIES

Correlative laboratory studies for this trial will focus on the modulation of immune response to SARS-CoV-2, clearance of virus, and modulation of immune cells in response to ibrutinib, and select senescence markers (i.e. clonal hematopoiesis, epigenetic age, and others) that are examined to be predictive of outcome. These results, using descriptive analyses, will be correlated between the ibrutinib plus supportive care and the placebo arm, and baseline values and change in values will be correlated with the primary or secondary outcomes. Samples will be collected at the following times:

- Screening
- Day 2 immediately pre-dose
- Cycle 2 Day 1
- End of Ibrutinib (± 3 days)
- 1, 3, 6, and 12 months post study entry (± 14 days)

In order to prevent viral transmission, patients who are discharged from the hospital will have follow-up labs collected at the OSU outpatient laboratory if they meet criteria for discontinuation of isolation at the outpatient setting. If they do not meet criteria for safe discontinuation of isolation per OSU guidelines, laboratory studies will not be obtained, and this will not be considered a protocol deviation. Samples for assays not performed in the clinical pathology laboratories (CPL) will be sent to the Experimental Hematology Laboratory (EHL) for analysis.

These samples will be used for the following assays:

- Measurement of viral clearance using PCR (from nasal pharyngeal swab in viral media) and serologic antibody testing (CPL):
- Measurement of immune cell subsets for absolute number, activation and exhaustion markers, and maturation using clinical immunome panel (CPL, EHL) at baseline and over time
- Measurement of senescence including epigenetic age (EHL), targeted sequencing for the presence of clonal hematopoiesis (EHL), and others at baseline (this will be done on residual DNA from material derived from immunophenotype/T-cell repertoire)
- Measurement of B/T-cell repertoire and IgM, IgA and IgG response to SARS-CoV-2 (CPL/EHL)

Ibrutinib for COVID 19

- Measurement of cytokines including IL6, IL1 β , TNF- α , and serum alternative multi-cytokine panel to be performed broadly in EHL (CPL/EHL)
- Measurement of serial and post-treatment T-cells to isolate and expand SARS-CoV2 specific T-cells, B-cells and other immune senescent changes (EHL)

Samples for the EHL will be collected and in some cases processed by the clinical trials processing laboratory (CTPL).

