12. STUDY CALENDAR^A

	Screening	Cycle 1 Day 1 ^I	Cycle 2 Day 1 ^I	End of Treatment (day 14 + up to 3 days if outpatient)	1 month post enrollment ^J	2 months post enrollment ^J	3 months post enrollment ^J	6 months post enrollment ^J	12 months post enrollment ^J
Informed Consent	X								
Medical History	X		X		X	X	X	X	X
Concomitant Medications	X	X	X	X	X	X	X	X	X
Adverse Events	X	X	X	X	X	X ^K	X ^K	X ^K	X ^K
Physical Exam	X	X	X	X					
Vital Signs^B	X	X	X	X					
EKG^C	X	X	X	X					
CBC with differential	X	X	X	X	X	X	X	X	X
Serum Chemistry^D	X	X	X	X	X	X	X	X	X
PT/PTT/INR, D- dimer, fibrinogen, LDH	X	X	X	X	X				
Hepatitis B,C Screening^E	X								
CRP, ferritin, troponin	X	X (daily)	X (daily)	X	X				
IL6, IFNγ, TNF	X		X	X					
Serum or Urine Pregnancy Testing	X								
Flow cytometry (Immunome)	X		X	X					
Total serum IgG, IgA, and IgM	X			X		X	X	X	X
Nasopharyngeal SARS-CoV-2 PCR^F	X			X	X (if negative will stop)	X (if negative will stop)	X (if negative will stop)		X (if negative will stop further testing)

Ibrutinib for COVID 19

					Further testing)	Further testing)	Further testing)		
Peripheral Blood for Correlative Laboratory Studies⁶	X	X	X	X	X	X	X	X	X
Ibrutinib or placebo			X						

- A. All research coordinator contact (consent, adverse events, concomitant medications) will be either by phone or over videoconference. Physical examination will be performed by the inpatient treatment team and does not have to be study personnel. For study participants who are discharged prior to completing 14 days, no daily labs will be performed at the outpatient setting and C2D1 labs will be performed on the day of discharge. Study participants will follow institutional inpatients/outpatient isolation initiation and discontinuation measures.
- B. Should include Oxygen saturations and O2 requirement. Consider continuous cardiac monitoring, especially for patients receiving concomitant medications with cardiac effects
- C. Consider continuous cardiac monitoring, especially for patients receiving concomitant medications with cardiac effects. All patients receiving hydroxychloroquine will be placed on telemetry as part of our standard institutional practice guidelines.
- D. Includes chem 10 and liver function panel. Should consider doing chemistry panel and CBC daily.

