- E. Includes hepatitis C Ab, hepatitis B antibody, surface antigen, and core antigen. Patients with positive surface antigen or core antibody should have hepatitis B DNA tested. Those with a positive core antibody and negative surface antigen may start treatment while awaiting hepatitis B DNA result given its long turnaround time. If the latter is positive, the study drug will be stopped.
- F. Will use currently available clinical methods, which may evolve during the course of the study. A positive COVID 19 PCR test at any facility within 10 days of screening is allowed.
- G. Please see section 11 for details on required samples. The correlative samples will be collected from standard clinical material that comes through the flow cytometry laboratory under [name]. Material (plasma, DNA, RNA) will be transferred to the EHL for studies not performed in clinical pathology.
- H. Ibrutinib will be administered daily for patients on the ibrutinib arm (Arm A) for a total of 2 cycles (14 days). Placebo will be administered to patients on the standard care arm (ARM B)
- I. During study drug administration, CBC and BMP should be collected daily. Liver function tests should be performed at least twice weekly.
- J. Post-discharge evaluations may be conducted by phone or videoconference. Laboratory studies will be obtained in the OSUCCC outpatient labs if patient meet criteria for discontinuation of isolation. Patients who are unable to return to OSU will be allowed to have labs performed locally and correlative/COVID related samples shipped to OSU if possible. This has to be approved by the study team. Labs can be performed \pm 7 days for timepoints after day 14.

K. Toxicity will continue to be assessed during phone assessments every other week in patients who do not have all toxicities that are possible drug-related resolved at the 1 month follow-up point.

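### A Kaplan-Meier median for time to viral clearance can only fall on a swab visit, because PCR is scheduled at day 14 and then at months 1, 2, 3 and 12

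*Combined protocol and SAP*

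**What the plan says.** Section 3.2 lists "Time to viral clearance" among the secondary endpoints, next to a separate endpoint for clearance at the end of therapy. It gives no definition, time origin or rule for dating clearance.

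Section 13, under Secondary Endpoints, says: "Time-to-event endpoints such as time to discharge and overall survival will be estimated for each arm using the method of Kaplan-Meier". Medians, estimates at chosen time points, or both are to follow with 95% confidence intervals. Time to viral clearance is not named there, and no interval-censored or discrete-time method appears.

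In the Section 12 calendar, the row "Nasopharyngeal SARS-CoV-2 PCR" is marked at screening, at "End of Treatment (day 14 + up to 3 days if outpatient"), at "1 month post enrollment", and at months 2, 3 and 12. It is blank at Cycle 1 Day 1, Cycle 2 Day 1 and month 6 (columns read by position in the extracted table). Footnote F adds: "A positive COVID 19 PCR test at any facility within 10 days of screening is allowed".

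Section 11 gives a different sample list: screening, Day 2, Cycle 2 Day 1, end of ibrutinib, and "1, 3, 6, and 12 months post study entry (± 14 days"). It says these samples serve several assays, including "Measurement of viral clearance using PCR (from nasal pharyngeal swab in viral media) and serologic antibody testing (CPL"), but its table of samples by assay has no PCR row.

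**The concern.** Discharge and death have dates that can be observed. Clearance on this schedule does not: it happened at some point after the last positive swab and no later than the first negative one. Kaplan-Meier applied to the date of the first negative swab treats that date as the event. On the calendar, every clearance between screening and the end of treatment is then dated day 14 or shortly after, and the reported time can only be too long.

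The Rationale in the synopsis, repeated in Section 4.6, expects ibrutinib to improve viral clearance or at least not to harm it. Section 4.5 names an impaired immune response to the virus as a risk. A report of 14 days in both arms would read as reassurance on that question when the two arms could differ by several days in either direction.

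**Working it through.** **Plan's own figure.** The documents state no figure for time to viral clearance, so there is none to reproduce. The stated 82.8% power concerns the primary endpoint only.

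**Inputs.**
- Visits at days 14, 30, 60, 90 and 365 (Section 12, months rounded).
- 33 patients per arm, from 66 randomized 1:1 (synopsis and Section 13).
- Assumed: exponential clearance with true median *m*, swabs exactly on schedule, no deaths, no missing swabs.

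**Width of the intervals.** About 14 days (screening to day 14), then 30 − 14 = 16, 60 − 30 = 30, 90 − 60 = 30 and 365 − 90 = 275 days.

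**When the median is day 14.** The curve first steps at day 14. With 17 of 33 negative it falls to 16/33 = 0.485, so the median is day 14. With 16 negative it stands at 17/33 = 0.515, and the median moves to a later visit. So P(median = day 14) = P(X ≥ 17), where X is binomial with n = 33 and p = 1 − 2^(−14/m).

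| True median *m* (days) | p, negative by day 14 | P(X ≥ 17) |
|---|---|---|
| 7 | 0.750 | 0.999 |
| 9 | 0.660 | 0.971 |
| 10 | 0.621 | 0.923 |
| 12 | 0.555 | 0.737 |
| 13 | 0.526 | 0.618 |

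**Both arms reported as day 14** (product of the two probabilities):
- 10 v 7 days: 0.923 × 0.999 = 0.92, with 62% v 75% negative at day 14.
- 12 v 9 days: 0.737 × 0.971 = 0.72, with 55% v 66% negative.
- 13 v 10 days: 0.618 × 0.923 = 0.57, with 53% v 62% negative.

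**When they are not tied.** The median then jumps to another visit. For 13 v 10 days, the slower arm alone moves past day 14 in (1 − 0.618) × 0.923 = 35% of trials. A true gap of 3 days is then shown as at least 30 − 14 = 16 days.

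**Simulation check.** In 2,000 trials per setting on the calendar schedule, the median was day 14 in 93% for a true median of 10 days and 73% for 12, in line with the table. With a Weibull shape of 2 in place of the exponential, the shares were 100% and 90%.

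**Denser reading of Section 11.** With swabs at days 2, 8, 14, 30, 90 and later, the simulated exponential medians still fall only on visit days. A true 4 days is reported as day 8 in over 99% of trials, 12 days as day 14 in 68%, and 20 days as day 30 in 86%.

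**What the proportion would show.** For 62.1% v 75.0% the difference is 12.9 points. Its standard error is √(0.621 × 0.379/33 + 0.750 × 0.250/33) = 0.113, so the 95% interval is about 12.9 ± 22.2 points, or −9 to 35. That displays the uncertainty which a tie at day 14 conceals.

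**The case against.** **The useful quantity is already planned.** Clearance at the end of therapy is a listed endpoint, and Section 13 allows estimates at specific time points in place of medians. With complete testing, the Kaplan-Meier value at day 14 is the proportion cleared by then. This stands. A reader might infer that the planned output as a whole hides any arm difference, but the documents do not support that: only the median and the event dates are affected.

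**Kaplan-Meier is inferred for this endpoint.** Section 13 gives discharge and survival as examples, and the one viral-clearance analysis it names is a proportion at discharge. That is correct, but the sentence is general and no other rule covers the endpoint. If the sentence does not apply, the endpoint has no stated analysis, and the same edit is needed.

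**A Turnbull estimate recovers little.** If patients share visit dates, it equals Kaplan-Meier at those dates and is undefined between them. For 10 v 7 days both medians would usually lie in the same first interval. This also stands: the gain is that the result is stated as an interval.

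**The schedule may be denser.** Section 11 can be read as adding swabs, and Sections 2.2 and 13 refer to clearance at discharge, for which the calendar has no swab. More swabs would shorten the intervals without removing them.

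**Early stopping.** A reader might infer that patients who stop drug early are swabbed earlier, which would bias the arm comparison. The documents do not establish this. The calendar column is fixed at day 14, and Section 7.7 keeps patients who discontinue on the calendar. The end-of-ibrutinib entry in Section 11 is at most ambiguous.

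**Conclusion.** The concern holds for the median and for the dating of events. If Section 13 is applied as written, the median time to viral clearance will be a visit date and will overstate the clearance time. For the pairs examined, both arms would show day 14 in about 92% (10 v 7 days), 72% (12 v 9) and 57% (13 v 10) of trials. A reader might infer that a tie is certain. That is true only in very large samples, not with 33 per arm.

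The percentages rest on assumed medians, exponential clearance, exact visit timing and complete testing. That only visit dates can be returned does not depend on the clearance distribution. Reading the curve at a visit as the proportion cleared does require complete testing, and Section 11 allows swabs to be skipped while isolation criteria are unmet.

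The reach is limited. Viral clearance is exploratory in the objectives and secondary only in Section 3.2, Section 13 calls these analyses largely descriptive, and the primary endpoint is untouched. It should still be corrected, because the plan as written yields a misleading number and the correction is small.

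**What to change.** In Section 13, state that no Kaplan-Meier median will be reported for this endpoint, and choose one of two routes:

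1. Analyse it as interval-censored between the last positive and the first negative swab, with a Turnbull estimate per arm and the median given as an interval. State the time origin, since the qualifying positive test may precede enrolment.
2. Replace it with the proportion PCR-negative at end of treatment, which is already a listed endpoint, and at month 1, with the between-arm difference and its 95% confidence interval.

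The second route is the simpler and uses what the schedule can measure. Separately, reconcile the Section 11 sample list with the Section 12 calendar so that the PCR dates are unambiguous.

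The cost is about one sentence in Section 13 and one scheduling clarification. No swabs, visits or patients are added. The downside is that the median can no longer be quoted as a single day.
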